- Patients whose platelet count decreases to <140,000 mm³ should begin weekly platelet monitoring, and patient whose platelet count decreases to <75,000 mm³ should have platelets monitored every 2 to 3 days. Patients whose platelet count decreases to <50,000 mm³ should discontinue drug and undergo daily platelet monitoring; consultation with a hematologist is also recommended.

Renal

- Patients with concern for renal toxicity, spot urine UPCR and/or spot UACR should be obtained. Patients with UPCR >50% from baseline or 1.5x ULN should be monitored at least every 2 weeks.
- Study drug should be discontinued if patients experience an unexplained, confirmed increase in serum creatinine of 0.3 mg/dL above baseline; unexplained, confirmed 25% decline in eGFR from baseline; or new-onset hematuria, albuminuria (UACR ≥250 mg/g), or proteinuria (≥UPCR 500 mg/g) confirmed on repeat testing.

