9.2.3 Interim Analysis

No formal interim analyses are planned for this study other than descriptive analyses required for the SRC to review accumulating safety information. Interim safety reviews and lipid analyses (sponsor only) will initially occur when approximately 12 patients have received their first study drug injection and have two weeks of follow-up data available. Subsequent analyses will occur with the accrual of each 12 new patients who have two week follow-up data available with a final review when the last 12 patients have two week follow-up data available.

Guidelines for interim study stoppage by the SRC will be based on safety parameters and the cumulative evidence of treatment group imbalances as follows:

- Clinically relevant signs or symptoms of similar nature occur in 3 or more patients in a treatment group that, in the opinion of the Investigator, warrants stopping based on concerns of patient safety.
- Two or more patients experiencing a non-cardiovascular SAE or 4 or more patients experience severe AEs.
- There is evidence of clinically significant increases in the following:
 - liver tests, defined as 3 × ULN (confirmed with repeat testing) in either ALT or AST; or 2 × ULN in either ALP or bilirubin, in 3 or more patients in a treatment group.
 - o confirmed platelet count decreases to <140,000 mm³
 - o confirmed increases in serum creatinine of 0.3 mg/dL above baseline

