#### 3.6.2 Clinical Laboratory Tests

Clinical safety chemistry, hematology, coagulation, and urinalysis will be collected at each study visit. Fibrinogen, cytokine and complement activation sampling will be collected at Day 1, Day 8, Day 15, Day 22, Day 29, Day 36, Day 43, Day 57 and Day 85 or early termination. hsCRP will be collected at Day 1, Day 8, Day 15, Day 22, Day 29, Day 36, Day 43, Day 57 and Day 85 or early termination. Thyroid-stimulating hormone (TSH), hemoglobin A1c (HbA1c), and serology will be collected in the Screening Visit.

Observed values and changes from baseline will be presented at each scheduled visit and baseline by laboratory test.

The primary endpoint is the incidence of clinically significant laboratory abnormalities, based on changes from baseline in hematology, clinical safety chemistry, and urinalysis test results. The incidence of abnormalities will be summarized with counts and percentages of patients for selected parameters grading by Common Terminology Criteria for Adverse Events (CTCAE) Version 5.0 if appropriate.

Laboratory	CTCAE Term	Grade 1	Grade 2	Grade 3	Grade 4
Chemistry	Alanine aminotransferase increased	>ULN - 3.0 x ULN if baseline was normal;	>3.0 - 5.0 x ULN if baseline was normal;	>5.0 - 20.0 x ULN if baseline was normal;	>20.0 x ULN if baseline was normal;
		1.5 - 3.0 x baseline if baseline was abnormal	>3.0 - 5.0 x baseline if baseline was abnormal	>5.0 - 20.0 x baseline if baseline was abnormal	>20.0 x baseline if baseline was abnormal
	Aspartate aminotransferase increased	>ULN - 3.0 x ULN if baseline was normal;	>3.0 - 5.0 x ULN if baseline was normal;	>5.0 - 20.0 x ULN if baseline was normal;	>20.0 x ULN if baseline was normal;
		1.5 - 3.0 x baseline if baseline was abnormal	>3.0 - 5.0 x baseline if baseline was abnormal	>5.0 - 20.0 x baseline if baseline was abnormal	>20.0 x baseline if baseline was abnormal

Laboratory	CTCAE Term	Grade 1	Grade 2	Grade 3	Grade 4
	Blood bilirubin	Total Bilirubin	Total Bilirubin	Total Bilirubin	Total Bilirubin
	increased	>ULN - 1.5 x ULN if baseline was normal;	>1.5 - 3.0 x ULN if baseline was normal;	>3.0 - 10.0 x ULN if baseline was normal;	>10.0 x ULN if baseline was normal;
		> 1.0 - 1.5 x baseline if baseline was abnormal	>1.5 - 3.0 x baseline if baseline was abnormal	>3.0 - 10.0 x baseline if baseline was abnormal	>10.0 x baseline if baseline was abnormal

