	Alkaline phosphatase increased	>ULN - 2.5 x ULN if baseline was normal;	>2.5 - 5.0 x ULN if baseline was normal;	>5.0 - 20.0 x ULN if baseline was normal;	>20.0 x ULN if baseline was normal;
		2.0 - 2.5 x baseline if baseline was abnormal	>2.5 - 5.0 x baseline if baseline was abnormal	>5.0 - 20.0 x baseline if baseline was abnormal	>20.0 x baseline if baseline was abnormal
	Creatinine increased	>ULN - 1.5 x ULN	>1.5 - 3.0 x baseline; >1.5 - 3.0 x ULN	>3.0 x baseline; >3.0 - 6.0 x ULN	>6.0 x ULN
	CPK increased	>ULN - 2.5 x ULN	>2.5 x ULN - 5 x ULN	>5 x ULN - 10 x ULN	>10 x ULN
	Hyperkalemia	Potassium	Potassium	Potassium	Potassium
		>ULN - 5.5 mmol/L	>5.5 - 6.0 mmol/L	>6.0 - 7.0 mmol/L	>7.0 mmol/L
	Chronic kidney	eGFR	eGFR	eGFR	eGFR
	disease	<lln -="" 60
ml/min/1.73 m2 or proteinuria 2+ present; urine protein/creatinine >0.5'.</lln>	59 - 30 ml/min/1.73 m2	29 - 15 ml/min/1.73 m2	<15 ml/min/1.73 m2
Hematology	Anemia	Hemoglobin (Hgb)	Hemoglobin (Hgb)	Hemoglobin (Hgb)	
		<lln -="" 10.0="" dl;
<lln -="" 6.2="" l;
<lln -="" 100="" g="" l<="" td=""><10.0 - 8.0 g/dL; <6.2 - 4.9 mmol/L; <100 – 80 g/L	<8.0 g/dL; <4.9 mmol/L; <80 g/L		</lln></lln></lln>	<10.0 - 8.0 g/dL; <6.2 - 4.9 mmol/L; <100 – 80 g/L	<8.0 g/dL; <4.9 mmol/L; <80 g/L	
	Hemoglobin increased	Hemoglobin > ULN &	Hemoglobin > ULN &	Hemoglobin > ULN &	
		Increase in >0 - 2 g/dL	Increase in >2 - 4 g/dL	Increase in >4 g/dL	
	White blood cell decreased	<lln -="" 3000="" mm3;
<lln -="" 10e9="" 3.0="" l<="" td="" x=""><3000 - 2000/mm3; <3.0 - 2.0 x 10e9 /L	<2000 - 1000/mm3; <2.0 - 1.0 x 10e9 /L	<1000/mm3; <1.0 x 10e9 /L	</lln></lln>	<3000 - 2000/mm3; <3.0 - 2.0 x 10e9 /L	<2000 - 1000/mm3; <2.0 - 1.0 x 10e9 /L	<1000/mm3; <1.0 x 10e9 /L
	Platelet count decreased	<lln -="" 75,000="" mm3;
<lln -="" 10e9
/L</lln></lln>	<75,000 - 50,000/mm3; <75.0 - 50.0 x 10e9 /L	<50,000 - 25,000/mm3; <50.0 - 25.0 x 10e9 /L	<25,000/mm3; <25.0 x 10e9 /L

For the other parameters, the incidence of abnormalities (as defined by normal ranges) prior to the first dose of study drug and after the first dose of study drug will be summarized with counts and percentages of subjects.

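### The SAP's renal laboratory table has no 0.3 mg/dL creatinine-rise or 25% eGFR-decline count, so some patients who meet the protocol's own renal criteria receive no grade in the primary laboratory endpoint

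*SAP*

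**What the plan says.** SAP 3.6.2 states: "The primary endpoint is the incidence of clinically significant laboratory abnormalities, based on changes from baseline" in hematology, chemistry and urinalysis. It then says how this is tabulated: "The incidence of abnormalities will be summarized with counts and percentages of patients for selected parameters", graded by CTCAE version 5.0 where appropriate. Parameters without a CTCAE row are counted as abnormal by normal range, before and after first dose.

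The renal rows of the CTCAE table are:

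- **Creatinine.** Grade 1 is above ULN up to 1.5 x ULN, with no baseline criterion. Grade 2 is ">1.5 - 3.0 x baseline; >1.5 - 3.0 x ULN". Grade 3 is ">3.0 x baseline; >3.0 - 6.0 x ULN". Grade 4 is above 6 x ULN.
- **Chronic kidney disease.** Grade 1 is eGFR from below LLN down to 60, or proteinuria, including a urine protein/creatinine ratio above 0.5. Grade 2 is "59 - 30 ml/min/1.73 m2". The higher grades are lower absolute bands. No grade uses a percent decline.

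The protocol measures renal change against the patient's own baseline. Section 8.1: "Study drug should be discontinued if patients experience an unexplained, confirmed increase in serum creatinine of 0.3 mg/dL above baseline". The same sentence gives "unexplained, confirmed 25% decline in eGFR from baseline" and new-onset hematuria, albuminuria (UACR at or above 250 mg/g) or proteinuria (UPCR at or above 500 mg/g), confirmed on repeat. Section 9.2.3, in the guidelines for the Safety Review Committee, lists "confirmed increases in serum creatinine of 0.3 mg/dL above baseline" under the heading of clinically significant increases.

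**The concern.** The endpoint is defined by clinical significance and change from baseline. For creatinine, the protocol says in 9.2.3 what change it regards as clinically significant. The SAP gives no other rule for deriving clinical significance, and its incidence table uses cut-offs that do not contain this one. A patient can therefore meet the protocol's renal criterion and receive no creatinine grade.

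Where this occurs, the error is an under-count in a primary safety endpoint. Each group has 12 patients, so one uncounted patient is 1/12 = 8.3 percentage points of that arm's incidence.

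**Working it through.** The plan gives no figure to reproduce, because the sample size is stated as not power-based. The check applies the SAP's grading rule to the protocol's thresholds. The documents give no creatinine ULN and no eGFR LLN, so both are assumptions shown as ranges.

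**Creatinine.** Let B be baseline and d the rise, both in mg/dL.

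1. The baseline part of Grade 2 is not met when B + d ≤ 1.5B, that is B ≥ 2d.
2. Grade 1 is not met when B + d ≤ ULN, that is B ≤ ULN − d.
3. Both hold for some B only if 2d ≤ ULN − d, that is d ≤ ULN/3.

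For d = 0.3, the ungraded baselines run from 0.6 to ULN − 0.3:

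| Assumed ULN | Ungraded baselines (0.1 steps) | Largest rise that can be ungraded (ULN/3) |
|---|---|---|
| 0.9 | 0.6 only | 0.30 |
| 1.0 | 0.6–0.7 | 0.33 |
| 1.1 | 0.6–0.8 | 0.37 |
| 1.2 | 0.6–0.9 | 0.40 |
| 1.3 | 0.6–1.0 | 0.43 |
| 1.4 | 0.6–1.1 | 0.47 |

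Examples at ULN 1.2:

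- 0.8 to 1.1 is 1.1/0.8 = 1.375 x baseline and below ULN: no grade.
- 0.5 to 0.8 is 1.6 x baseline: Grade 2, although below ULN.
- 1.0 to 1.3 is above ULN: Grade 1.

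The normal-range rule does not help. It covers only parameters without a CTCAE row, and a value at or below ULN is normal anyway.

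**eGFR.** A 25% fall leaves 0.75 x baseline. It stays at or above LLN, and so ungraded, when baseline ≥ LLN/0.75. That is 60/0.75 = 80 for LLN 60, or 90/0.75 = 120 for LLN 90. For example, 110 falls to 82.5, which is ungraded at LLN 60 and Grade 1 at LLN 90. Since only eGFR below 60 is excluded at screening, at LLN 90 a patient who enters at 60 to 89 and does not change has a value in that same Grade 1 band.

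**Urine criteria.** The SAP's protein/creatinine entry above 0.5 matches the protocol's 500 mg/g apart from the boundary value, if the unit is g/g. UACR has no CTCAE row. Protocol Appendix B lists it under urinalysis, so if counted it falls under the normal-range rule, without the 250 mg/g cut.

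**The case against.** The strongest reply is that the gap is narrow and the events are visible elsewhere.

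**Narrowness stands.** A reader might infer that the SAP grades creatinine only against ULN, or that large rises could go unseen. The table does not support either reading. Grades 2 and 3 also use the patient's own baseline, and any rise above ULN/3 receives a grade. A patient ungraded for creatinine might also be graded through the eGFR row, depending on LLN and baseline.

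**Visibility elsewhere stands in part.** A reader might infer that a drug-stopping renal change would vanish from the report. It should not:

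- SAP 3.6.2 presents change from baseline by visit, and SAP 3.6 lists all individual data.
- Protocol 9.2.1 adds listings of clinically significant abnormalities.
- Protocol 8.2 requires an adverse event when an abnormality leads to action with study drug. SAP 3.6.1 tabulates adverse events leading to treatment discontinuation. If judged related, the event also counts in the other primary endpoint.

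None of these gives a by-arm count of patients meeting the threshold. The visit summaries are means, medians, SDs and ranges (SAP 3.1.4), and listings are not incidences. The discontinuation route is unreliable after the second and last dose on Day 29. Four of the eight scheduled visits after Day 1 (Days 36, 43, 57 and 85) fall after it, when no dose remains to be stopped. Reporting then depends on a need for intervention or on the investigator's judgment.

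**No analysis rule is broken.** Protocol 9.2.1 allows CTCAE grading where appropriate. Section 8.1 guides individual discontinuation without defining clinical significance, which 8.2 leaves to the investigator. Section 9.2.3 does attach the term to the 0.3 mg/dL rise, but as a committee guideline, and it names no eGFR criterion. The link to the endpoint is therefore firm for creatinine and weaker for eGFR. Even so, the SAP already counts patients by size of change elsewhere, for QTc (above 30 and 60 msec) and in the hemoglobin-increased row.

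**Conclusion.** The point holds in limited form. The SAP's graded renal rows contain neither the protocol's 0.3 mg/dL creatinine criterion nor its 25% eGFR criterion. Confirmed creatinine rises from 0.3 mg/dL up to ULN/3 (0.30 to 0.47 mg/dL for assumed ULNs of 0.9 to 1.4) can go ungraded for creatinine. So can 25% eGFR falls from baselines of at least 80 or 120, for assumed LLNs of 60 or 90. The existence of the gap follows from the rules; its width depends on the laboratory limits, which the documents do not give.

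Three stronger inferences are not supported:

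- **A miss rate.** The documents give no creatinine distribution and no expected frequency of such rises. The share of patients whose baseline lies in the ungraded range would not be a miss rate even if it were known.
- **Urine findings going uncounted.** The protein/creatinine criterion is already graded, and UACR probably falls under the normal-range rule.
- **An established renal signal for this product.** The reference list includes a report of acute kidney injury with an antisense oligonucleotide against PCSK9, but the text shown does not say how the protocol uses it.

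The change should still be made, because this is a primary safety endpoint in small arms and the remedy is cheap.

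**What to change.** Reconcile SAP 3.6.2 with protocol 8.1 and 9.2.3. Keep the CTCAE rows. Beside them, add counts and percentages of patients by treatment group who after first dose meet:

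- the confirmed creatinine rise of 0.3 mg/dL above baseline;
- the confirmed 25% eGFR decline from baseline;
- for completeness, the UACR cut of 250 mg/g.

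State that these counts belong to the primary laboratory table. Define confirmation by repeat testing, which is how the protocol describes it for urine findings (8.1) and liver tests (9.2.3). Include unscheduled retests explicitly, because SAP 3.1.2 keeps only the value closest to the target day within each visit window and could drop the confirming sample. Also state whether explained changes are counted, since 8.1 requires the creatinine and eGFR changes to be unexplained and 9.2.3 does not.

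The cost is SAP wording and one extra table from data already collected. Some fluctuation within the normal range will be counted in every arm, including placebo, which gives the comparison. No new clinical threshold is proposed; the counts use those the protocol already states.

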- 15. Abnormal PT, aPTT, or INR at the screening visit.
- 16. Concomitant antiplatelet or anticoagulation medication. Allowable are low-dose aspirin (81 mg or less, daily) for CVD risk reduction, or PRN for occasional pain relief. Other antiplatelet drugs (e.g., P2Y12 inhibitors) and all anticoagulants are exclusionary.
- 17. Except as noted above, patients who have a clinically significant disorder that, in the opinion of the Investigator, could contraindicate the administration of study drug, affect compliance, interfere with study evaluations, or confound the interpretation of study results
- 18. History of drug or alcohol abuse within the past year.
- 19. Previous treatment with CIVI 007.
- 20. Participation in another clinical study of an investigational agent or device concurrently or within 1 month prior to the Screening Visit or use of an investigational agent within 1 month or 5 half-lives (if known), whichever is longer, prior to the Screening Visit.
- 21. Donation of blood from 3 months prior, plasma 2 weeks prior, and platelets 6 weeks prior to the Screening Visit.
- 22. Any other findings that, in the opinion of the Investigator, would compromise the participant's safety or participation in the study.

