- e Vital signs include pulse rate, blood pressure, respiration rate, and temperature. Blood pressure should be obtained in a seated position after the participant has been sitting or at least 5 minutes. Blood pressure at the Screening Visit should be obtained in both arms, and the arm with the highest value should be used for ongoing monitoring throughout the rest of the study. If an automated assessment is performed, the same machine should be used for the participant throughout the study whenever possible. Care should be taken to ensure an appropriate cuff size is utilized.
- f Height will be measured only at the participant's Screening Visit.
- g A urine microscopic examination will be performed when the dipstick result is abnormal (i.e., positive for blood, leukocyte esterase, or nitrites).
- Pregnancy tests are for women of childbearing potential only. A serum pregnancy test will be performed at screening. Urine pregnancy test will be conducted at all other visits. Unscheduled serum pregnancy testing will be performed for confirmation of positive urine pregnancy testing. FSH tests are for all postmenopausal women who are not surgically sterile; FSH testing will be performed once at screening.
- ⁱ Drugs of abuse along with thyroid-stimulating hormone, HbA1c, and serology (HBsAg, HBV, HCV, and HIV) will be measured at the participant's Screening Visit. Serology testing will be HBsAg, HCV, and HIV, with confirmatory testing for positive HCV and HIV Ab screens.
- ^j The fasting lipid panel includes LDL-C, non-HDL-C, TC, TGs, HDL-C, and VLDL-C. Fasting will be defined as no food or caloric beverage for at least 10 hours (±2 hours) prior to sample collection. Patients will be permitted to have water. LDL-C will be estimated.
- ^k Fasting apolipoproteins include apoB, apoA1, and Lp(a). Beta quant LDL is beta-quantification measurement of LDL-C. Fasting will be defined as no food or caloric beverage for at least 10 hours (±2 hours) prior to sample collection. Patients will be permitted to have water.
- PK, cytokine panel, and complement activation sampling will be performed on dosing days and at each study visit during the Follow-up Period. For each of the dosing days, samples will be drawn at pre-dose (-1 hour), 3 hours (±1 hour) post-dose, and at 8 hours (±1 hour) post-dose.

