# 3.1.3 Definition of Baseline

Baseline for all efficacy and safety variables will be defined as the last scheduled value obtained prior to the first dose of study drug. If the measurement at this visit is missing, the last measurement prior to the first dose of study drug will be used as baseline. The scheduled baseline visit for all efficacy and safety variables is Day 1 pre-dose.

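### For laboratory tests without CTCAE grading, the SAP sets out-of-range incidence over 1 or 2 pre-dose tests beside incidence over 8 to 12 post-dose tests, so a rise is expected in every arm without any drug effect

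*SAP*

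**What the plan says.** SAP 3.6.2 grades selected chemistry and hematology parameters by CTCAE. For all other parameters it gives counts and percentages of subjects by "incidence of abnormalities (as defined by normal ranges) prior to the first dose of study drug and after the first dose of study drug". It does not limit either period to one result, require an in-range baseline or define a new abnormality.

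On sampling, the same section states: "Clinical safety chemistry, hematology, coagulation, and urinalysis will be collected at each study visit". It continues: "Fibrinogen, cytokine and complement activation sampling will be collected at Day 1, Day 8, Day 15, Day 22, Day 29" and later visits, and likewise "hsCRP will be collected at Day 1, Day 8, Day 15, Day 22, Day 29" and later visits. SAP 3.1.3 places the Day 1 result before dosing: "The scheduled baseline visit for all efficacy and safety variables is Day 1 pre-dose".

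For cytokines and complement, a footnote to the schedule in Protocol Appendix A adds draws on Days 1 and 29: "For each of the dosing days, samples will be drawn at pre-dose (-1 hour), 3 hours (±1 hour) post-dose", with a further draw at 8 hours.

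Protocol 4.2, exclusion 15, excludes patients with "Abnormal PT, aPTT, or INR at the screening visit".

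SAP 3.6.2 bases the laboratory primary endpoint on changes from baseline in hematology, clinical safety chemistry and urinalysis.

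**The concern.** The chance of at least one out-of-range result grows with the number of results. A two-period table whose periods differ four- to twelvefold in the number of tests invites a before-after reading that partly reflects sampling density.

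The analytes affected include some inside the primary endpoint. Going by Protocol Appendix B, GGT, sodium, BUN, albumin, the white-cell differential, dipstick blood and the urine albumin ratio all fall outside the CTCAE table. For these, the two-period count is the only tabulation of out-of-range incidence that the SAP specifies.

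The table also lacks a within-patient link. A patient out of range in both periods and a patient newly out of range after dosing each add one to the post-dose count, so the table does not identify change from baseline, on which the endpoint is based.

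**Working it through.** The plan states no figure on this point, so there is none to reproduce.

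**Step 1: count the tests** (SAP 3.1.3 and 3.6.2; Protocol Section 6 and Appendix A).

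| Analytes | Before first dose | After first dose |
|---|---|---|
| Chemistry, hematology, coagulation, urinalysis | Screening, Day 1 = 2 | Days 8, 15, 22, 29, 36, 43, 57, 85 = 8 |
| Fibrinogen, hsCRP | Day 1 = 1 | the same 8 |
| Cytokines, complement | Day 1 pre-dose = 1 | Day 1 (2) + Days 8, 15, 22 (3) + Day 29 (3) + Days 36, 43, 57, 85 (4) = 12 |

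The footnote says "PK, cytokine panel, and complement activation sampling will be performed on dosing days and at each study visit during the Follow-up Period". Read narrowly, that omits Days 8, 15 and 22 and leaves 9 draws after dosing. The schedule grid, Protocol Section 6 and SAP 3.6.2 all include those days, which gives 12. TSH, HbA1c and serology have no scheduled post-dose sample, so the point does not apply to them.

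**Step 2: expected incidence with no drug effect.** Let *p* be the chance that a single result is out of range. This is an assumption, because the documents give no rate. For *k* independent results, P(at least one) = 1 − (1 − p)^k. At p = 5%:

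- k = 1: 5.0%
- k = 2: 1 − 0.95² = 9.8%
- k = 8: 1 − 0.95⁸ = 33.7%
- k = 12: 1 − 0.95¹² = 46.0%

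Results within a patient are correlated. To allow for this, let a result be out of range when a normal variable exceeds its threshold, with correlation ρ between any two results from one patient, and average 1 − (1 − q)^k over patients, where q is the patient's own rate. For 2 tests against 8:

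| Assumed p | Independent, before v after | ρ = 0.7, before v after |
|---|---|---|
| 1% | 2.0% v 7.7% | 1.7% v 4.4% |
| 5% | 9.8% v 33.7% | 8.0% v 16.8% |
| 10% | 19.0% v 57.0% | 15.3% v 28.8% |

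At p = 5% and ρ = 0.9 the figures are 6.8% v 10.9%. The gap closes only if a patient's results never differ between tests. In an arm of 12, the p = 5%, ρ = 0.7 case is 12 × 0.080 = 1.0 against 12 × 0.168 = 2.0 expected patients.

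For cytokines and complement at p = 5% and ρ = 0.7, 1 test against 12 gives 5.0% v 19.9% (17.7% after dosing on the 9-draw reading). This presumes that reference ranges exist for them, and the documents give none.

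**Step 3: effect of exclusion 15.** If abnormal there means outside the normal range, an enrolled patient's Screening PT, aPTT and INR are in range, and only Day 1 can fill the pre-dose cell. Given an in-range Screening result, p = 5% and ρ = 0.7 give 3.2% before and 13.4% after.

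**Step 4: what an arm of 12 would show** (simulation, 2 tests against 8, no drug effect, p = 5%). A given arm shows a rise with probability 0.89 to 0.90 if results are independent and 0.66 at ρ = 0.7. All four arms do so with probability 0.64 and 0.19. At p = 1% and ρ = 0.7 these are 0.31 and about 0.01.

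**The case against.** The strongest defence is that the SAP specifies no before-after difference or test. SAP 3.6 summarizes safety by treatment received, and Protocol 3.2 gives placebo the role of separating drug effects from study conditions. Within the post-dose column the scheduled draws are equal across arms, so active against placebo is fair provided follow-up is similar. This stands, and it confines the point to the before-after reading.

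Other outputs also limit the harm. SAP 3.6.2 presents values and changes from baseline at each visit, Protocol 9.2.1 lists clinically significant abnormalities, and those reported as adverse events are tabulated by arm. This stands too, though none of these counts how many patients moved out of range.

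A third objection is that any replacement still relies on a placebo arm of 12. That is true. The standard error of a difference between two arms, √(2 × P × (1 − P)/12), is about 15 points at P = 16.8% and 19 points at P = 33.7%. New abnormalities also accumulate by chance: at p = 5% with no drug effect, 33.7% (independent) or 13.4% (ρ = 0.7) of patients in range at Day 1 would be counted over 8 draws. The replacement removes the unequal periods but adds no precision.

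Two stronger readings are not supported:

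- A reader might infer that the table must show a rise in every arm. Only the expected incidence rises, and Step 4 shows that ties and falls in single arms are common.
- A reader might infer that the most extreme ratios bear on the primary endpoint. Coagulation, fibrinogen, cytokines and complement are safety variables outside it, and hsCRP is an exploratory endpoint. The affected primary-endpoint analytes are the ungraded chemistry, hematology and urinalysis tests, at 2 against 8.

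**Conclusion.** The point holds as a minor one. The test counts follow from the documents, apart from the 9-or-12 ambiguity for cytokines and complement. The direction of the expected bias does not depend on the assumed rate.

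Its size does. For 2 tests against 8, it runs from 1.7% v 4.4% (p = 1%, ρ = 0.7), under one patient per arm in either period, to 19.0% v 57.0% (p = 10%, independent). These figures assume no drug effect, a constant rate over visits, complete follow-up and every result in a period counting. The last is the natural reading of subject counts per period, though the SAP does not say so outright. If the pre-dose period means baseline only, the imbalance becomes 1 against 8.

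Unscheduled retests and safety-driven extended visits would widen the gap, because the post-dose period is given no end. Since the comparison with placebo, the by-visit summaries and the adverse event tables are untouched, the documents do not support a claim that the safety analysis as a whole is biased.

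**What to change.** In SAP 3.6.2, replace the before/after incidence for ungraded parameters with new abnormalities:

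- Among patients in range at Day 1 pre-dose, give the number and percentage with at least one out-of-range value at scheduled post-dose draws through Day 85, low and high separately.
- Show each arm and pooled CIVI 007 beside placebo, with a note that the figures are to be read against placebo only. For a given analyte the number of scheduled draws is the same in all arms: 8, or up to 12 for cytokines and complement.
- Report patients out of range at Day 1 in a separate shift line.
- Give the out-of-range percentage at each visit, including Day 1, so that any before-after reading sets one visit against another.

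The cost is SAP wording and some extra table programming, with no new data. The denominator becomes smaller, and values seen only at unscheduled visits drop out of the count, though they remain in the individual listings that SAP 3.6 already provides.
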